between the two study arms. For instance, if the pre-drug PA diastolic pressure measurements have a SD of 4 mmHg, we will have 80% power to detect a difference of +/- 2.4 mmHg in PA diastolic pressure. If the pre-drug average PA diastolic pressure is 12 mmHg, this means a 20% change in the treatment arm is detectable assuming there is no change in the control arm. Each primary endpoint will be tested at the two-sided 5% significance level.

Inducibility Endpoints: The primary hypothesis in Aim 3 tests whether RyR2 inhibition with dantrolene reduces the susceptibility to ventricular arrhythmias. Susceptibility to ventricular arrhythmias is measured by testing the inducibility of VT/VF using programmed ventricular stimulation.

Primary Analysis Aim 3:

Inducibility of Ventricular Arrhythmias: Ventricular arrhythmias are defined as monomorphic or polymorphic VT, or VF. The primary endpoint is either a sustained hemodynamically stable ventricular arrhythmia of ≥ 10 seconds duration or an unstable ventricular arrhythmia requiring termination (with pacing or defibrillation), or two episodes of non-sustained ventricular arrhythmia defined as an episode lasting 3-9 seconds. To maximize statistical power, the primary analysis utilizes an ordinal endpoint that measures the relative inducibility based on the stage of the induction protocol and the arrhythmia induced (**Table 5**). Multivariable regression models are built. Univariable logistic regression modeling will be used to test whether treatment with dantrolene is associated with the category of inducibility (ordinal endpoint) measured post-study drug with adjustment for the stage of inducibility measured pre-study drug. Multivariable modeling includes additional adjustment for age (continuous), sex, amiodarone exposure (yes/no), change in beta-agonist exposure, and time from start of drug to post-drug stimulation protocol. Models will be evaluated for goodness-of-fit, and internally validated for calibration/discrimination with bootstrap.

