Secondary Analyses Aim 3: A binary endpoint of inducibility (yes/no) is analyzed using logistic regression with the same covariate adjustment described for the primary analysis. Another secondary analysis tests the idea that RyR2 inhibition with dantrolene may alter inducible ventricular arrhythmias due to changes in conduction and refractoriness and hemodynamic improvement. An ordinal variable defining the cardiac rhythm stability class is analyzed (**Table 6**) using multivariable ordinal logistic regression. A secondary analysis will explore all the ventricular arrhythmia susceptibility endpoints for an interaction between cardiomyopathy type (ischemic versus non-ischemic) and treatment with dantrolene. Definitions: 1) Stable monomorphic VT is mean arterial pressure at 10 seconds (MAP_{10}) or immediately prior to termination of >50 mmHg; 2) Unstable VT is MAP_{10} or prior to termination of <50 mmHg; 3) Pleomorphic VT is more than one QRS morphology for 3 or more consecutive beats during the same VT episode; and 4) Polymorphic VT is a continually changing QRS morphology.⁵⁴

Sample Size and Power Aim 3: Primary Endpoint: The sample size selected for this trial was calculated to adequately power the analysis of the inducibility endpoint in Aim 3 which is an ordinal variable (Table 5). With $N=84$ patients (randomized to placebo and treatment in 1:2 ratio) with an expected 50% of patients in the placebo arm non-inducible, and 10% in each of the other categories, the study will achieve 80% power to detect an odds ratio (OR) of 0.3 at the two-sided significance level of 5%. With an anticipated 20% withdrawal rate prior to study drug, up to a total number of 105 patients will be enrolled in the study to ensure statistical power. Secondary Endpoints: 1) The binary status of inducibility (yes/no). With an effective sample size of 84, the study provides 80% power to detect an OR of 0.25, and a 70% power to detect an OR of 0.3 at the two-sided significance level of 5%.

Assessment of Safety (Aim 3): An interim analysis will be performed by the DSMB when 50% of the target enrollment is reached to test for an association between dantrolene or placebo and significant adverse events/harm. In order to preserve statistical power for the secondary analyses, the interim analysis will not include early stopping rules for efficacy. Although none of our Phase I pre-clinical or clinical data have raised

Table 5. Ordinal Inducibility Endpoint

	Category	

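### The fully adjusted logistic model for binary inducibility fits at least seven predictors to about 25 to 27 events; ordinary maximum likelihood would overstate a real drug effect, and a Firth fit largely corrects this for a small loss of nominal power

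*Combined protocol and SAP*

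**What the plan says.** All of this is in Section 10.0 of the combined protocol and SAP, under the primary and secondary analyses and the sample size for Aim 3.

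- **Binary endpoint.** "A binary endpoint of inducibility (yes/no) is analyzed using logistic regression with the same covariate adjustment described for the primary analysis". No estimator, penalty or small-sample correction is named.
- **Covariates carried over.** The primary analysis tests treatment "with adjustment for the stage of inducibility measured pre-study drug". The fuller model then adds more terms: "modeling includes additional adjustment for age (continuous), sex, amiodarone exposure (yes/no), change in beta-agonist exposure, and time from start of drug to post-drug" stimulation. How pre-drug stage is coded is not stated; Table 5 has ten levels.
- **Safeguard.** "Models will be evaluated for goodness-of-fit, and internally validated for calibration/discrimination with bootstrap". Nothing is said about correcting the treatment coefficient.
- **Planning assumptions.** The ordinal power statement uses an "expected 50% of patients in the placebo arm non-inducible". For the binary endpoint: "With an effective sample size of 84, the study provides 80% power to detect an OR of 0.25", with 70% at an odds ratio of 0.3, two-sided 5%.

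**The concern.** Maximum-likelihood logistic regression is biased away from no effect when events are few relative to the number of coefficients. Here there are fewer than four events per predictor. If dantrolene works, the adjusted odds ratio from this model would tend to look better than the truth, and the planned bootstrap validation is not described as shrinking it.

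What is at stake is the size of the reported effect, and any later trial planned on it. Required sample size varies roughly with the inverse square of the log odds ratio. An overstatement of 13.5% would therefore give a trial about 1/1.135² = 0.78 of the size needed, roughly a fifth too small.

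**Working it through.** **Inputs from the plan.** 28 placebo and 56 dantrolene patients; placebo inducibility 1 − 0.50 = 0.50; odds ratio (OR) 0.25 or 0.3; two-sided 5%. Withdrawals before study drug are already covered: 84/0.80 = 105 enrolled.

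**1. The plan's power reproduces.** With placebo odds of 1, the dantrolene risk is p₂ = OR/(1 + OR). The pooled two-proportion formula is

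z = [(p₁ − p₂) − 1.96·√(p̄(1 − p̄)(1/28 + 1/56))] / √(p₁(1 − p₁)/28 + p₂(1 − p₂)/56).

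- OR 0.25: p₂ = 0.200, p̄ = 0.300, z = (0.300 − 1.96 × 0.1061)/0.1086 = 0.85, power 80.2%.
- OR 0.3: p₂ = 0.231, p̄ = 0.321, z = (0.269 − 1.96 × 0.1080)/0.1100 = 0.52, power 70.0%.

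The stated 80% and 70% are therefore unadjusted two-proportion powers.

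**2. Expected events.**

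- OR 0.25: 28 × 0.5 + 56 × 0.200 = 25.2.
- OR 0.3: 28 × 0.5 + 56 × 0.231 = 26.9.
- No effect: 84 × 0.5 = 42.

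**3. Predictors.** Treatment, pre-drug stage (one term if linear), age, sex, amiodarone, change in beta-agonist exposure and time from drug: seven. Events per predictor: 25.2/7 = 3.6 and 26.9/7 = 3.8.

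**4. Simulation of the seven-predictor model.** 28:56 patients, 4,000 trials per scenario, maximum likelihood (ML) against Firth on the same data. The documents give no covariate effects, so three assumed strengths were used: none; moderate (largest log-OR coefficient 0.7, others up to 0.3); strong (largest 1.5, others up to 0.5). OR 0.3 was not run with strong covariates. LR is the likelihood-ratio test, penalised for Firth.

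| True OR, covariates | Mean events | Log-OR bias, ML → Firth | Geometric mean OR, ML → Firth | MSE, ML → Firth | LR power, ML → Firth |
|---|---|---|---|---|---|
| 0.25, none | 25.2 | +13.5% → +0.9% | 0.207 → 0.247 | 0.419 → 0.284 | 78.8% → 77.3% |
| 0.25, moderate | 26.9 | +13.3% → −0.2% | 0.208 → 0.251 | 0.505 → 0.338 | 74.6% → 71.6% |
| 0.25, strong | 30.1 | +17.8% → +0.4% | 0.195 → 0.249 | 0.741 → 0.452 | 65.8% → 60.6% |
| 0.3, none | 27.0 | +11.3% → −0.4% | 0.262 → 0.302 | 0.389 → 0.283 | 68.1% → 65.2% |
| 0.3, moderate | 28.5 | +13.8% → +0.6% | 0.254 → 0.298 | 0.469 → 0.324 | 64.3% → 60.8% |

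The bias is present even when no covariate is prognostic. The cut in mean squared error (MSE) runs from 1 − 0.283/0.389 = 27% to 1 − 0.452/0.741 = 39%. With Wald tests, Firth loses about 4 to 6 points of power.

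**5. No drug effect** (5,000 trials each, no and moderate covariate effects, 42 events). The mean ML log OR was about 0.00. Type I error with the LR test was 5.5 to 6.2% for ML and 4.4 to 4.9% for Firth. A Wald test after Firth was conservative (3.2 to 3.6%).

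**6. Second, smaller simulation** (500 trials per scenario). ML bias was about 13 to 16%, Firth bias about 1 to 3%, and the MSE reduction about 30%. Nominal power was 3 to 4 points lower with Firth. Type I error was 5.8 to 6.8% (ML) against 4.2 to 4.4% (Firth). Once both tests were set to the same size, Firth's power was equal or slightly higher. The Monte Carlo error of these type I rates is about √(0.05 × 0.95/500) = 1 point.

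**7. Pre-drug stage as a ten-level factor** (nine terms; non-prognostic covariates, 1,500 trials). ML bias rose to 31% at OR 0.25 and 28% at OR 0.3, and about 94% of trials had at least one very large coefficient. Firth bias was 4% and 3%, and LR power fell from 80.1% to 75.5% and from 67.1% to 62.1%.

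**8. Treatment and pre-drug stage only.** Events per predictor are 25.2/2 = 12.6 and 26.9/2 = 13.5. ML bias was about 3 to 4% with non-prognostic covariates, and up to about 8% in the smaller simulation.

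**The case against.** The strongest reply is that this is a choice between bias and power on a secondary endpoint. Several parts of it stand.

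- **The change is not free.** A reader might infer that penalisation costs nothing. In the main simulation nominal power fell in every scenario. A separate check also found Firth's mean predicted risk about 1 percentage point above the observed rate, a small but real cost where calibration is to be assessed. The power loss, however, appears to be mostly the removal of slight type I inflation, because power at equal test size was no worse.
- **The plan has a smaller model.** For the primary endpoint, the test of treatment adjusts for pre-drug stage alone, and the longer list is additional. A reader might infer that whatever odds ratio is reported must be inflated. The documents do not support that; the problem belongs mainly to the full adjustment.
- **The inference is less affected than the estimate.** At OR 0.25 with non-prognostic covariates the bias is 1.573 − 1.386 = 0.187, against a standard deviation of √(0.419 − 0.187²) = 0.62, or about 0.3 of it. Coverage of the ordinary 95% Wald interval was 94 to 95%.
- **Maximum likelihood is an inference.** It is the usual meaning of unqualified logistic regression, but the plan does not say it.

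None of this removes the reason to prefer an estimator with less bias and smaller mean squared error.

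**Conclusion.** The point holds for the fully adjusted binary model read as maximum likelihood. At the plan's design effects a true log odds ratio is overstated by about 11 to 18%, and by about 28 to 31% if pre-drug stage enters as a ten-level factor. The event count follows from the plan's inputs. The size of the bias also depends on the assumed covariate distributions and strengths.

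Two stronger readings are not supported. One is that the bias creates a false claim of efficacy: with no drug effect the estimate is unbiased, and type I inflation is slight. The other is that it undermines the trial's main result: the binary endpoint is secondary, and the sample size was set on the ordinal one.

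One uncertainty remains. The plan does not say which Table 5 categories count as inducible. If only those meeting the primary endpoint do, events would be fewer; the bias in that case was not computed.

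**What to change.** State in the SAP that the binary inducibility model, with the plan's listed covariates, is fitted by Firth-penalised logistic regression. Name the penalised likelihood-ratio test and the profile-likelihood interval, not Wald. Enter pre-drug stage as a single linear score. The list should be called the plan's covariates, not baseline covariates, because change in beta-agonist exposure and time from drug are determined after dosing.

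Describe the 80% and 70% as unadjusted two-proportion power and restate power for the adjusted model. Under the assumptions above, the penalised likelihood-ratio test gives about 61 to 77% at OR 0.25 and 61 to 65% at OR 0.3. Much of the shortfall from the stated figures is already present with maximum likelihood (66 to 79% and 64 to 68%).

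The cost is a short SAP addition, a standard R package, and nominal power about 1.5 to 5 points lower on this secondary endpoint. No change to sample size or data collection is needed.

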6.6 Ventricular Arrhythmia Induction Protocol

A standardized induction protocol is performed using programmed ventricular stimulation from the RV apex. The protocol is based on a prior study evaluating a range of induction protocols used to test inducibility before and after AAD administration in the EP lab.³⁹ Sedation and vasopressor infusion is maintained at constant levels throughout the study protocol and, any changes warranted for clinical care will be documented. The pacing cycle length is 8 beats followed by extrastimuli (ES) and a 3 second rest period. The basic cycle length of the pacing drive train (S1 – S1) is 600 ms (100 bpm). The first extrastimulus (S2) is introduced at 300 ms and decremented by 10 ms to VERP or 200 ms. S2 is then set to a coupling interval (S1 – S2) of VERP (or 200 ms) + 20 ms and a second extrastimulus (S3) added at a coupling interval of S1-S2 + 50 ms and scanned to refractoriness or a minimum coupling interval of 200 ms. The second extrastimulus is then set to its VERP + 20 ms and a third extrastimulus (S4) added at an initial coupling interval (S3 – S4) of S2 – S3 + 50 ms and scanned in to refractoriness or 200 ms. Thus up to 3 extrastimuli are added and the minimum coupling interval will not be shorter than 200 ms. The induction protocol is stopped when: 1) the primary endpoint is met, or 2) the induction protocol has been completed. The primary endpoint is an episode of sustained VT that lasts \geq 10 seconds or two episodes of non-sustained ventricular arrhythmia defined as VT or VF that lasts 3-9 seconds.

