Least inducible	0	No sustained VT/VF or NSVT
	1	1 episodes of NSVT with S4
↓	2	1 episodes of NSVT with S3
↓	3	1 episodes of NSVT with S2
↓	4	2 episodes of NSVT with S4*
↓	5	2 episodes of NSVT with S3*
↓	6	2 episodes of NSVT with S2*
↓	7	Sustained VT/VF with S4
Most inducible	8	Sustained VT/VF with S3
	9	Sustained VT/VF with S2

*the category assigned for 2 episodes of NSVT is based on the extrastimulus used to induce the second episode of NSVT.

Table 6. Secondary analysis of rhythm stability

	Category	
Least Stable	1	Ventricular Fibrillation
	2	Polymorphic VT
↓	3	Pleomorphic VT
↓	4	Unstable Monomorphic VT
Most Stable	5	Stable Monomorphic VT
	6	No Inducible VT/VF

safety concerns, and no adverse events have been observed, we planned the assessment of safety, which will be based on the frequency of adverse events. Other safety data such as blood pressure will be considered. All adverse events recorded during the study will be summarized. See Ethical Aspects of the Proposed Research for DSMB.

Respiratory Mechanics and Ventilation Endpoints: To monitor adequacy of ventilation, maintain safety, and measure the effect of dantrolene administration on ventilation, the anesthesiologist will monitor respiration and oxygenation as is standard of care for all patients during procedures and surgeries. The primary endpoint of the Respiratory Mechanics substudy is the incidence of the addition of respiratory support, including bag/mask ventilation, CPAP, BiPAP, LMA, or tracheal intubation, from the time of study drug administration until 120 minutes after study drug administration. Placement of airway support devices is at the discretion of the attending anesthesiologist and will be based on standard safety parameters such as oxygen saturation, adequacy of ventilation, and airway obstruction. Secondary endpoints include additional markers of respiratory mechanics and strength including negative inspiratory force, dynamometer measured grip strength, accelerometer (respiratory rate, tidal volume, minute ventilation), markers of gas exchange (arterial pH, pCO₂, pO₂, base excess), and electrolytes. Tidal volume, respiratory rate, and minute ventilation parameters will be continuously collected (recorded every minute) as available. We will summarize these data prior to study drug administration and at 10 and 20-minutes after dantrolene administration.

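### Table 6 has no level for non-sustained arrhythmia, so short polymorphic runs can score as less stable than sustained unstable monomorphic VT

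*Combined protocol and SAP*

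**What the plan says.** Section 10.0, Secondary Analyses Aim 3, plans a multivariable ordinal logistic regression of rhythm stability: "An ordinal variable defining the cardiac rhythm stability class is analyzed". The levels are in "Table 6. Secondary analysis of rhythm stability", from least to most stable: VF (1), "Polymorphic VT" (2), pleomorphic VT (3), "Unstable Monomorphic VT" (4), stable monomorphic VT (5) and "No Inducible VT/VF" (6).

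The definitions beside the analysis include "Polymorphic VT is a continually changing QRS morphology" and "Pleomorphic VT is more than one QRS morphology for 3 or more consecutive beats during the same VT episode". Neither gives a minimum time in seconds. Stable and unstable VT are separated by a mean arterial pressure of 50 mmHg, read at 10 seconds or just before termination.

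Three other places give a duration rule, and none refers to Table 6:

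- Section 1.5 (background) takes 10 seconds as the definition of an inducible arrhythmia.
- Section 6.6 counts VT of at least 10 seconds, or two episodes of "non-sustained ventricular arrhythmia defined as VT or VF that lasts 3-9 seconds".
- Section 10.0, Inducibility Endpoints, uses the same two criteria and adds unstable arrhythmia that has to be terminated.

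Table 5, the primary ordinal endpoint, gives non-sustained VT its own levels (1-6), all below sustained VT/VF (7-9).

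**The concern.** Table 6 drops the distinction between sustained and non-sustained arrhythmia on which Table 5 is built. A patient whose induced rhythm shrinks from a sustained, hemodynamically unstable monomorphic VT to short self-terminating runs has improved on the primary scale. The same patient can move down on the stability scale if the short runs are polymorphic.

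This analysis is meant to describe how dantrolene changes the arrhythmias that remain inducible. If the scoring of 3-9 s runs is settled only after the data are seen, that choice can change the strength of the result and, in some patterns, its sign.

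**Working it through.** **Step 1. Score the same change on both tables.** Start from sustained monomorphic VT with pressure below 50 mmHg, induced with S4: Table 5 = 7, Table 6 = 4.

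| Post-drug finding | Table 5 | Table 6, morphology read literally | Table 6, Sections 6.6 and 10.0 endpoint | Table 6, Section 1.5 10-second rule |
|---|---|---|---|---|
| Two polymorphic runs of 3-9 s, second with S4 | 4 (better by 3) | 2 (worse by 2) | 2 (worse by 2) | 6 (better by 2) |
| One polymorphic run of 3-9 s, with S4 | 1 (better by 6) | 2 (worse by 2) | 6 (better by 2) | 6 (better by 2) |

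Two short runs satisfy the endpoint as defined in Sections 6.6 and 10.0, so under those operative definitions they cannot be category 6. Only the background sentence in Section 1.5 would put them there. For a single run the documents support either 2 or 6, on opposite sides of 4.

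**Step 2. Illustrative size.** The plan states no rate, effect or power for Table 6, so there is no figure to reproduce. As a starting mix I used the post-ablation series described in Section 1.5: of 165 patients, 38 had sustained monomorphic VT, 9 VF and 34 NSVT, which leaves 165 - 38 - 9 - 34 = 84 with none. NSVT is 34/(38 + 9 + 34) = 34/81 = 42% of the inducible patients.

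Assumptions that are mine: half of sustained monomorphic VT is unstable; a share q of NSVT is polymorphic (scored 2 literally); the rest of NSVT is scored 5.

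The measure is w = P(drug more stable) + half of P(tie), and win odds = w/(1 - w). Above 1 favors the drug.

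*Pattern A, general benefit.* A share s of patients moves one step (sustained or VF to NSVT, NSVT to none). Example with s = 50%, q = 50%, counts per 165 in categories 1, 2, 4, 5, 6:

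- Placebo: 9, 17, 19, 36, 84. Drug: 4.5, 20.25, 9.5, 29.75, 101.
- w = (4.5×4.5 + 20.25×17.5 + 9.5×35.5 + 29.75×63 + 101×123)/165² = 15,009/27,225 = 0.551, so win odds are 1.23. With a separate NSVT level they are 1.34.

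Over s = 50-70% and q = 30-70%, win odds are 1.20-1.37 read literally and 1.34-1.50 with the level. Simulated power (56 versus 28 patients, Wilcoxon test, two-sided 5%) is about 12-28% read literally and 21-43% with the level. The benefit is diluted, not reversed.

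*Pattern B, conversion only.* A share f of sustained monomorphic VT becomes NSVT and nothing else changes. Example with f = 100%, q = 50%:

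- Literal reading. Placebo as above; drug 9, 36, 0, 36, 84. w = (9×4.5 + 36×17.5 + 36×63 + 84×123)/27,225 = 13,270.5/27,225 = 0.487, so win odds are 0.95.
- With the level (categories 1, 4, 5, NSVT, 6). Placebo 9, 19, 19, 34, 84; drug 9, 0, 0, 72, 84. w = (9×4.5 + 72×64 + 84×123)/27,225 = 14,980.5/27,225 = 0.550, so win odds are 1.22.

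For f = 50-100% and q = 50-70%, win odds are 0.90-0.98 read literally and 1.11-1.22 with the level. At q = 30% the literal win odds are about 1.0: the benefit disappears without reversing.

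**The case against.** **The documents do put duration into inducibility.** A reader might infer that any single 3-second polymorphic run is ranked below sustained unstable VT. The text does not fix that. Section 1.5 requires 10 seconds, and Sections 6.6 and 10.0 require two short episodes, so a single run can fairly be category 6. This stands: for single runs the defect is an ambiguity. It does not rescue two short runs, which meet the endpoint.

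**The two tables measure different things.** Table 5 grades ease of induction and Table 6 the kind of rhythm, so disagreement is not in itself an error, and a shift from monomorphic to polymorphic VT may be what Table 6 should detect. This stands in part. It is a reason to grade morphology among sustained episodes, not to leave the place of 3-9 s runs unstated. Nor is Table 6 purely morphological, because categories 4 and 5 are split by blood pressure.

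**The numbers are soft.** The cited series counts monomorphic VT as sustained above 30 seconds, not 10, and by its title concerns ischemic cardiomyopathy, while this trial also enrolls other patients. The polymorphic share and shift patterns are assumed, and an unadjusted rank test stands in for the planned regression. All of this stands, so the figures are illustrative only.

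**Scoring short runs as category 6 would give more power** (about 33-66% in Pattern A). That is true, but power alone should not choose the scale. It would merge a met endpoint with no arrhythmia, and Section 1.5 itself reports that inducible NSVT marked recurrence.

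**Conclusion.** The gap is real and confined to a secondary analysis. Table 6 has no place for non-sustained arrhythmia. Under the operative endpoint definitions, two short polymorphic runs score 2, below sustained unstable monomorphic VT at 4, while Table 5 records the same change as an improvement. A single short run is unresolved between 2 and 6.

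A reader might infer that a drug benefit would generally appear as harm. The calculations do not support that. With a general one-step benefit the literal scoring weakens the result, with power of about 12-28% against 21-43%. Reversal needs a narrower pattern: mostly conversion of sustained monomorphic VT to NSVT that is at least half polymorphic. The documents give no rates from which to judge how likely that is. The primary inducibility endpoint already separates sustained from non-sustained arrhythmia and is not affected.

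**What to change.** Before unblinding, amend the Table 6 wording in three respects:

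1. Apply categories 1-5 only to episodes of at least 10 seconds or those requiring termination.
2. Add a level, *non-sustained only (3-9 s), any morphology*, between categories 5 and 6. This follows Table 5, where even two non-sustained episodes rank below any sustained one.
3. State which episode is classified when several are induced.

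Episode duration is already needed to score Table 5, so no new data are required. The price is that morphology within non-sustained runs is no longer graded in this variable; it can be tabulated descriptively by arm.

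### The placebo distribution given as the basis for N=84 does not fit Table 5 (its shares total 140%); separately, the stated 80% power is about 73% in an unadjusted calculation with 50% in category 0

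*Combined protocol and SAP*

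**What the plan says.** Section 10.0, Sample Size and Power Aim 3, names this endpoint as the one that fixed the trial's size: "The sample size selected for this trial was calculated to adequately power the analysis of the inducibility endpoint in Aim 3". The inputs are 84 patients in a 1:2 ratio (28 placebo, 56 dantrolene), a two-sided 5% level, OR 0.3, 80% power, and a placebo arm "with an expected 50% of patients in the placebo arm non-inducible, and 10% in each of the other categories".

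Table 5 lists ten ordered categories, from 0 ("No sustained VT/VF or NSVT") to 9 ("Sustained VT/VF with S2"). Categories 1 to 3 are a single episode of non-sustained VT (NSVT), 4 to 6 are two episodes, and 7 to 9 are sustained arrhythmia.

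Primary Analysis Aim 3 counts a patient as meeting the endpoint on a sustained or unstable arrhythmia, "or two episodes of non-sustained ventricular arrhythmia defined as an episode lasting 3-9 seconds". Section 6.6 also requires two episodes. A single NSVT episode therefore does not meet the endpoint, although Table 5 places it above category 0.

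Even the simplest Aim 3 model adjusts for the pre-drug inducibility stage. The power paragraph names no method, does not say whether OR 0.3 is marginal or adjusted, and claims no gain from adjustment.

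**The concern.** There are two separate problems. First, the planning distribution does not describe the scale to which it is tied, and no assignment of the word non-inducible to Table 5's categories makes the stated shares add up. Second, 80% is not what a standard unadjusted calculation gives under the reading closest to the wording, in which non-inducible is category 0 and the other categories are the remaining nine.

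This is the calculation offered for choosing 84 patients. A reader cannot tell which distribution, which definition of non-inducible or which kind of OR lies behind it. Under the category 0 reading without adjustment, the chance of missing a true OR of 0.3 is about 27%, against the 20% implied.

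**Working it through.** **Step 1: the shares.**
- Category 0 non-inducible, nine others: 50% + 9 × 10% = 140%.
- Categories 0 to 3 non-inducible, six others: 50% + 6 × 10% = 110%.
- The total is 100% only with five others: 50% + 5 × 10%, a six-level scale.

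**Step 2: reproducing the 80%.** The closed-form proportional-odds (Whitehead) formula is

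power = Φ(|ln OR| × √V − 1.96), with V = [n₁n₂/(3N)] × (1 − Σp̄³),

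where p̄ is the category share averaged over both arms. Here n₁n₂/(3N) = 28 × 56/(3 × 84) = 6.222 and |ln 0.3| = 1.204. A variant of the leading constant, n₁n₂N/[3(N+1)²] = 6.077, lowers each result by about one point.

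The formula returns the plan's figure if the placebo shares are entered where p̄ belongs:

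| Placebo shares used as p̄ | Σp̄³ | V | Power (variant constant) |
|---|---|---|---|
| Six levels, 50% + 5 × 10% | 0.130 | 5.413 | 80.0% (79.1%) |
| Ten levels, 50% + 9 × 5.56% | 0.1265 | 5.435 | about 80% (79.2%) |
| Shares as written, total 140% | 0.134 | 5.388 | 79.8% (78.9%) |

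**Step 3: the same formula with averaged shares.** Under OR 0.3, the dantrolene odds of lying above category 0 are 1 × 0.3, so 0.3/1.3 = 23.1% lie above it and 76.9% are in category 0. For ten levels:
- equal weights: Σp̄³ = 0.2562, V = 4.628, power 73.6% (72.6% with the variant constant);
- weights 1:2: Σp̄³ = 0.3141, V = 4.268, power 70.1% (69.1%).

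The six-level results are within about 0.1 point of these.

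**Step 4: simulation without the approximation.** Tie-corrected Wilcoxon test, proportional odds, 28 versus 56, two-sided 5%, 200,000 runs, 50% in category 0:
- OR 0.3: 73.0% (ten levels) and 72.9% (six levels); type I error about 5%.
- OR 0.265: about 80% for both.
- A likelihood-ratio version for ten levels gave about 71% (1,500 runs).

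**Step 5: 50% spread over categories 0 to 3.** The remainder of the 50% is split equally over categories 1 to 3, with 8.33% in each of categories 4 to 9, at OR 0.3:

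| Share in category 0 | 12.5% | 20% | 30% | 35% | 40% | 45% |
|---|---|---|---|---|---|---|
| Unadjusted power | 83% | 83% | 81% | 79–80% | 78% | 75–76% |

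**Step 6: adjustment for the pre-drug stage.** The documents give no pre/post correlation, so these are illustrations on assumed values (50% in category 0, 2,000 runs each):
- If 0.3 is a marginal OR, power is 79%, 80%, 82% and 95% at latent correlations of 0.4, 0.5, 0.6 and 0.8.
- If 0.3 is already the adjusted OR, power is about 66 to 72% for pre-drug effects of 0.5 to 2.0 log-odds per SD.

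**Step 7: neighbouring figures.** The binary endpoint reproduces with 50% inducible on placebo and the pooled-variance formula: 80.2% at OR 0.25 and 70.0% at OR 0.3, as stated. The enrolment figure also holds: 84/0.8 = 105. Neither shows which categories hold the 50%.

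**The case against.** The strongest reply is that 80% can be recovered. Step 2 shows the closed-form formula returning 79 to 80% from the placebo shares, even from the set that totals 140%. A reader might infer that the impossible total makes 80% underivable, or that it explains the drop to 73%. Neither follows. A valid six-level distribution also gives 73%, so correcting the sum alone would leave the gap. What stands against the plan is that the 80% returns only when one arm's shares replace the two-arm average. That this was done is an inference, since no method is named.

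A second reply is that the text may have been written for a six-level scale and not updated to Table 5. That is plausible but also inferred. It would explain the mismatch without making the assumption fit the endpoint.

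A third is that 73% describes a test the plan does not use, because the model adjusts for the pre-drug stage. This stands as a limit on the 73%. It does not supply the missing support for 80%: the power paragraph relies on no such gain, and Step 6 shows that the direction depends on which OR is meant.

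Finally, with 50% in category 0 and the OR taken in the opposite direction, simulated power is about 81%. The stated hypothesis is a reduction in inducibility, so this is not the planned alternative.

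**Conclusion.** The mismatch is certain: the stated shares total 140% over Table 5's categories, or 110% on the more generous definition of non-inducible. The power finding is conditional. With 50% in category 0, proportional odds, 28 versus 56 and no covariate, power at OR 0.3 is about 73%, and 80% requires an OR of about 0.265. With the 50% spread over categories 0 to 3, power is about 75 to 83%, so some valid distributions do support the claim.

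A reader might go further and conclude that the trial is underpowered or that 84 patients are too few; about 99 to 102 would be needed for 80% under the category 0 reading without adjustment. The documents do not support that conclusion, because the planned model is adjusted and the information needed to compute its power is not given. The planning statement is wrong as written and its power figure unsupported. It should be corrected, but it is not a reason to change the design.

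**What to change.** Keep N=84 and the planned analysis. In Section 10.0, Sample Size and Power Aim 3:

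1. Replace the planning assumption with ten placebo shares for Table 5 that sum to 100%.
2. Say which categories count as non-inducible: 0 only, or 0 to 3.
3. Name the power method, using two-arm average proportions or simulation.
4. Say whether OR 0.3 is marginal or adjusted for the pre-drug stage.
5. Restate the power or detectable OR on those inputs. With 50% in category 0 and no adjustment gain assumed, this is about 73% at OR 0.3, or 80% at OR about 0.265. Otherwise, give the recomputed value with its category split and any pre/post correlation shown.

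The cost is SAP wording and one recalculation, with no extra patients. The downside is that the stated figure may become slightly less favourable, and that a figure for the adjusted model needs an explicit correlation assumption.
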